#### **5.3.9.3 Abortions**

Any spontaneous abortion should be classified as an SAE (as the Sponsor considers spontaneous abortions to be medically significant events), recorded on the AE eCRF, and reported to the Sponsor immediately (i.e., no more than 24 hours after learning of the event; see Section 5.3.8).

Any induced abortion due to maternal toxicity and/or embryo-fetal toxicity should also be classified as an SAE, recorded on the AE eCRF, and reported to the Sponsor immediately (i.e., no more than 24 hours after learning of the event; see Section 5.3.8).

Elective abortion not associated with toxicity (e.g., induced abortion for personal reasons) does not require expedited reporting but should be reported as outcome of pregnancy on the Clinical Trial Pregnancy Reporting Form.

#### **5.3.9.4 Congenital Anomalies/Birth Defects**

Any congenital anomaly/birth defect in a child born to a female HV/patient or female partner of a male HV/patient exposed to study drug should be classified as an SAE, recorded on the AE eCRF, and reported to the Sponsor immediately (i.e., no more than 24 hours after learning of the event; see Section 5.3.8).

### **5.4 FOLLOW-UP OF SUBJECTS AFTER ADVERSE EVENTS**

#### **5.4.1 Investigator Follow-Up**

The Investigator should follow each AE until the event has resolved to baseline grade or better, the event is assessed as stable by the Investigator, the HV/patient is lost to follow-up, or the HV/patient withdraws consent. Every effort should be made to follow all SAEs considered to be related to study drug or trial-related procedures until a final outcome can be reported.

During the study period, resolution of AEs (with dates) should be documented on the AE eCRF and in the HV's/patient's medical record to facilitate source data verification. If, after follow-up, return to baseline status or stabilization cannot be established, an explanation should be recorded on the AE eCRF.

All pregnancies reported during the study should be followed until the pregnancy outcome, and reported according to the instructions provided in Section 5.3.9.

#### **5.4.2 Sponsor Follow-Up**

For SAEs, non-serious AEs of special interest, and pregnancies, the Sponsor or a designee may follow up by telephone, fax, electronic mail, and/or a monitoring visit to obtain additional case details and outcome information (e.g., from hospital discharge summaries, consultant reports, autopsy reports) in order to perform an independent medical assessment of the reported case.

### **5.5 POST-STUDY ADVERSE EVENTS**

The Investigator is not required to actively monitor HV/patients for AEs after the end of the AE reporting period (defined as end of follow-up period: 28 days after last study drug dose for HVs and 6 weeks after last study drug dose for patients).

If the Investigator becomes aware of any other SAE occurring after the end of the AE reporting period, and the event is believed to be related to prior study drug treatment, the event should be reported directly to the Sponsor or its designee, either by faxing or by scanning and emailing the SAE Reporting Form using the fax number or email address provided to investigators.

## **5.6 EXPEDITED REPORTING TO HEALTH AUTHORITIES, INVESTIGATORS, INSTITUTIONAL REVIEW BOARDS, AND ETHICS COMMITTEES**

The Sponsor will promptly evaluate all SAEs and non-serious AEs of special interest against cumulative product experience to identify and expeditiously communicate possible new safety findings to investigators, IRBs, IECs, and applicable health authorities based on applicable legislation.

To determine reporting requirements for single AE cases, the Sponsor will assess the expectedness of these events using the following reference document:

- [RO7020531 IB](#)

The Sponsor will compare the severity of each event and the cumulative event frequency reported for the study with the severity and frequency reported in the applicable reference document.

Reporting requirements will also be based on the Investigator's assessment of causality and seriousness, with allowance for upgrading by the Sponsor as needed.

## **6. STATISTICAL CONSIDERATIONS AND ANALYSIS PLAN**

The analysis of complete data for the study will be performed when all HVs/patients have either completed the follow-up period or have discontinued early from the study, all data from the study are in the database and have been cleaned and verified, and the database is locked.

This is an exploratory study for which no formal hypothesis testing will be done and thus no adjustment for multiplicity of testing will be performed.

### **6.1 DETERMINATION OF SAMPLE SIZE**

#### **Part 1: SAD and MAD in Healthy Volunteers**

The current planned study design and sample size complies with standard safety review rules applied in single and multiple ascending dose studies.

#### **Part 2: Chronic Hepatitis B Patients**

Sample size is determined based on clinical judgment and practical considerations. With eight patients treated with RO7020531, there is a 90% chance to observe at least one AE if the underlying event incidence rate is 25% in the patient population.

## **6.2 REPLACEMENT POLICY (ENSURING ADEQUATE NUMBERS OF EVALUABLE SUBJECTS)**

HVs/patients prematurely discontinued from the study for non-safety reasons may be replaced to ensure adequate numbers of evaluable HVs/patients. HV/patient replacement numbers will be provided by Roche or its designee. For more details see Section 4.7.1.

The decision to replace a withdrawn HV/patient will be made at the discretion of the Sponsor and the investigator for Part 1, and at the discretion of the Sponsor for Part 2.

## **6.3 SUMMARIES OF CONDUCT OF STUDY**

The number of HVs/patients who are randomized, discontinued, or complete the study treatment and/or the entire study (including follow up period) will be summarized by treatment. Reasons for premature study withdrawal (treatment phase and follow up phase) will be listed and summarized by treatment. Enrollment and protocol deviations will be listed and evaluated for their potential impact on interpretation of study results.

## **6.4 ANALYSIS POPULATIONS**

### **6.4.1 Safety Analysis Population**

All HVs/patients who have received at least one dose of the study medication, whether prematurely withdrawn from the study or not, will be included in the safety analysis. HVs/patients will be analyzed according to the treatment actually received.

### **6.4.2 Pharmacokinetic Analysis Population**

A per protocol analysis including all HVs/patients randomized and adherent to the protocol will be performed. HVs/patients will be excluded from the pharmacokinetic analysis population if they significantly violate the inclusion or exclusion criteria, deviate significantly from the protocol or if data are unavailable or incomplete which may influence the PK analysis. Excluded cases will be documented together with the reason for exclusion. All decisions on exclusions from the analysis will be made prior to database closure.

### **6.4.3 Pharmacodynamic Analysis Population**

The analyses of PD data will include all HVs/patients who were randomized, received at least one dose of study medication (RO7020531 or placebo), and have PD data available. HVs/patients will be analyzed according to the treatment group to which they were randomized.

## **6.5 SUMMARIES OF TREATMENT GROUP COMPARABILITY**

Descriptive statistics will be generated for demographic and baseline disease characteristics including sex, race, ethnicity, origin (for Asian HVs/patients only), age, weight, height, body mass index, HBV DNA and HBsAg levels, and HBV history including but not limited to duration of HBV disease, previous HBV treatments, length of time on NUCs. Data for study drug administration and concomitant medication will be listed. The number of HVs/patients who were randomized, discontinued treatment period, completed treatment period, discontinued study and completed the study (including follow-up period) will be summarized.

## **6.6 PRIMARY AND SECONDARY STUDY VARIABLES**

The primary study variables are those measuring safety and tolerability. The PK and PD measures of the active metabolite RO7011785, following single and multiple doses of RO7020531, are secondary variables.

## **6.7 SAFETY ANALYSES**

All safety analyses will be based on the safety analysis population.

### **6.7.1 Adverse Events**

The original terms recorded on the eCRF by the Investigator for AEs will be standardized by the Sponsor by assigning preferred terms from the Medical Dictionary for Drug Regulatory Affairs (MedDRA). AEs will be summarized by mapped term and appropriate thesaurus level.

AEs will be described by individual listings and frequency tables broken down by body system.

### **6.7.2 Clinical Laboratory Test Results**

All clinical laboratory data will be stored on the database in the units in which they were reported. HV's/patient's listings and summary statistics at each assessment time will be presented using the International System of Units (SI units; Système International d'Unités). Laboratory data not reported in SI units will be converted to SI units before processing.

Laboratory test values will be presented by individual listings with flagging of values outside the normal ranges.

Safety analyses to determine if treatment groups are safe to proceed will use all available data reported from local and/or central laboratory results. Unscheduled local laboratory tests may be ordered per investigator discretion and may be used for the individual management of the HV/patient. A duplicate sample should simultaneously be sent to the central laboratory for analysis (Part 2 only).

### **6.7.2.1 Standard Reference Ranges and Transformation of Data**

Roche standard reference ranges, rather than the reference ranges of the Investigator, will be used for all parameters. For most parameters, the measured laboratory test result will be assessed directly using the Roche standard reference range. Certain laboratory parameters will be transformed to Roche's standard reference ranges.

A transformation will be performed on certain laboratory tests that lack sufficiently common procedures and have a wide range of investigator ranges, e.g., enzyme tests that include AST, ALT, and alkaline phosphatase and total bilirubin. Since the standard reference ranges for these parameters have a lower limit of zero, only the upper limits of the ranges will be used in transforming the data.

### **6.7.2.2 Definition of Laboratory Abnormalities**

For all laboratory parameters included, there exists a Roche predefined standard reference range. Laboratory values falling outside this standard reference range will be labeled "H" for high or "L" for low in HV/patient listings of laboratory data.

In addition to the standard reference range, a marked reference range has been predefined by Roche for each laboratory parameter. The marked reference range is broader than the standard reference range. Values falling outside the marked reference range that also represent a defined change from baseline will be considered marked laboratory abnormalities (i.e., potentially clinically relevant). If a baseline value is not available for a HV/patient, the midpoint of the standard reference range will be used as the HV/patient's baseline value for the purposes of determining marked laboratory abnormalities. Marked laboratory abnormalities will be labeled in the HV/patient listings as "HH" for very high or "LL" for very low.

### **6.7.3 Vital Signs**

Vital signs data will be presented by individual listings with flagging of values outside the normal ranges and flagging of marked abnormalities. In addition, tabular summaries will be used, as appropriate.

### **6.7.4 ECG Data Analysis**

ECG data will be presented by individual listings with flagging of values outside the normal ranges and flagging of marked and clinically significant abnormalities. In addition, tabular summaries will be used, as appropriate.

Summary descriptive statistics for the actual values and changes from baseline will be tabulated by nominal time for HR, QRS duration, PR and QTcF. For multiple measurements taken at a nominal time-point, the average of these measurements will be used as the value at that nominal time-point in all summaries. In addition, QTcF will be categorized at each time-point as  $\leq 450$  msec,  $>450-480$  msec,  $>480-500$  msec and  $>500$  msec and summarized. Similarly, a summary will be provided of the QTcF changes from baseline at each time-point categorized as  $<30$  msec,  $30-60$  msec, and  $>60$  msec. Changes of the overall ECG interpretation, T-wave and U-wave morphology will be summarized.

### **6.7.5 Concomitant Medications**

The original terms recorded on the HVs'/patients' eCRF by the investigator for concomitant medications will be standardized by the sponsor by assigning preferred terms.

Concomitant medications will be presented in summary tables and listings.

## **6.8 PHARMACOKINETIC ANALYSES**

Non-compartmental analysis using WinNonlin software will be used to calculate PK parameters where appropriate. Summary descriptive statistics of plasma PK parameters including  $C_{max}$ ,  $T_{max}$ ,  $AUC_{inf}$ ,  $AUC_{last}$  and  $t_{1/2}$  for RO7020531 and RO7011785 and additional metabolites including RO7018822 and RO7033805, will be presented by treatment arm including mean, SD, CV, medians and ranges. Where appropriate, data may be pooled and analyzed for example, all single dose data may be pooled. Listings, summary tables and graphs (individual plots and/or mean plots) by treatment group will be provided. Descriptive statistics of urine PK parameters for RO7020531 and RO7011785 and additional metabolites including RO7018822 and RO703380 will be presented, where available. PK and PD data from this study may be used to develop a population PK/PD model.

HVs/patients will be excluded from the PK analysis if data are unavailable which may influence the analysis (see Section 6.4.2). Where appropriate, listings and summary tables of tenofovir (including tenofovir alafenamide, if approved for HBV and applicable), entecavir, adefovir and telbivudine concentrations will be provided based on the sparse sampling throughout the study.

## **6.9 PHARMACODYNAMIC ANALYSES**

Summary descriptive statistics will be presented for the induction of cytokines, chemokines, and neopterin and of interferon-response genes separately by treatment arm. Exploratory analysis will be performed to assess the interferon-induced response under different dosing conditions. Graphical and statistical techniques including linear, nonlinear, and logistic regression will be used to explore potential relationships between dosing regimen, PK and PD.

## **6.10 EXPLORATORY ANALYSES**

All antiviral endpoints are considered exploratory for this study (Part 2 only). Summary descriptive statistics will be used to summarize the antiviral outcome measures of qualitative HBsAg, quantitative HBsAg actual and change from baseline, and HBeAg, anti-HBe and anti-HBs status at each of the time-points by treatment group. For Cohort 4, the outcome of antiviral response will additionally include quantitative HBV DNA level (actual and change from baseline). Status of HBsAg and HBeAg seroconversion, if any, and maintenance of HBV DNA levels less than 90 IU/mL (Cohorts 1, 2 and 3) will also be summarized. The findings from the resistance analyses will be listed for each patient selected for analysis.

Exploratory analysis may also be performed to identify markers and/or marker panels correlating with and/or potentially predictive of an in vivo PD response, the occurrence of certain AEs (to be defined) and/or changes in viral parameters.

A detailed exploratory analysis plan will be developed when initial study results (AE, viral/antiviral parameters in Part 2) have been reviewed.

### **6.10.1 Analyses of Antiviral Measures (Part 2 Only)**

Summary descriptive statistics will be used to summarize the antiviral outcome measures of qualitative HBsAg, quantitative HBsAg actual and change from baseline, and HBeAg, anti-HBe and anti-HBs status at each of the time-points by treatment group. Status of HBsAg and HBeAg seroconversion, if any, and maintenance of HBV DNA levels less than 90 IU/mL (Cohorts 1, 2 and 3) will also be summarized.

The findings from the resistance analyses will be listed for each patient selected for analysis.

### **6.10.2 Analysis to Support Dose-Escalation Decisions and Dose-Selection**

Bayesian adaptive methods such as continual re-assessment method (CRM) may be applied once a dose level in the SAD part, which is considered to be safe and also exhibits a response for at least one member of the screening panel of biomarkers (e.g., IL-10, IP-10) indicating activation of the TLR pathway, is identified to initiate dosing of MAD cohorts. However, model-based CRM dose-escalation approaches will only be considered as supporting information for the dose-escalation and/or dose selection. Clinical judgment will always take precedence in making the final decisions.

There are two main endpoints of this study: safety and characterization of TLR PD biomarker activity. Two types of modelling approaches for the next best dose recommendation may be explored in Part 1 MAD for HVs and Part 2 for CHB patients. Operating characteristics of both models will be compared to determine the appropriateness.

a) Based only on dose-limiting event (DLE) responses:

N-CRM with control for the probability of over-dosing, based on occurrence of a DLE may be applied to inform decision about the dose of RO7020531 to be given to the next cohort during dose-escalation. A DLE will be defined as any treatment-related adverse reaction as described in Section 3.1.2 (e.g., AE, laboratory abnormality, etc.) that would prevent another drug administration at the same dose level in a given HV/patient.

Details on the model/algorithm are given below. The relationship between the dose and the probability of observing a DLE will be described by the following two-parameter logistic regression model:

$$\text{logit}(p) = \log\left(\frac{p}{1-p}\right) = \alpha + \beta \log\left(\frac{\text{dose}}{\text{ref}}\right)$$

where  $p$  is the probability of observing a DLE at a given dose,  $\alpha$  is the log of the odds for  $p$  at the reference dose (ref, here equals to X mg, starting dose of MAD) and  $\beta$  is the change in the log odds for an e1-fold increase in dose (detailed discussion about this model parameterization can be found in [Neuenschwander et al 2008](#)).

The model will be estimated using a Bayesian framework; priors for  $\alpha$  and  $\beta$  will be specified using the data from the already completed cohorts of the SAD part of the study. Given the data, Markov Chain Monte Carlo (MCMC) sampling will be used for obtaining the posterior distribution of the model parameters.

After each cohort of HVs/patients completes dosing, the model will be updated with the DLE-observed occurrence and a new MTD will be defined as the dose such that:

- The probability of being within the target safety interval (of 20% to 35% DLE rate) is maximized and
- The probability of being within the excessive toxicity interval (above 35% DLE rate) is below 30%.

b) Dose-escalation based on dual endpoint (modelling both DLE and PD biomarker response)

This model may be flexibly applied based on the availability of the data for the panel of biomarkers constituting the result of activation the TLR pathway. The aim of the dual endpoint design is to estimate an optimal dose level which represents an optimal trade-off between safety and biomarker response.

For joint modelling of DLE and PD biomarker response (assuming correlation), the Bayesian approach developed by ([Bekele and Shen 2005](#)) and as implemented in the R package `crmPack` ([Bove et al 2016](#)) will be considered for the escalation process. A DLE for this model may be limited to any treatment mechanism of action (MOA)-related adverse reaction (e.g., severe flu-like symptoms, not tolerable and not manageable with

symptomatic treatment). Alternatively, another Bayesian dose-escalation approach modelling the two endpoints separately (assuming no correlation) may also be explored. In this, the biomarker response would be modelled as a linear log-log function of dose and a gain function applied to select the next best dose (Yeung et al 2015).

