### 3.1.1.2 Part 1: MAD in Healthy Volunteers

The trigger to start the first cohort in the MAD includes documentation of adequate safety and tolerability in the SAD. In addition, evidence in at least two subjects within a particular dose cohort exhibiting responses above placebo-defined baseline for select PD biomarkers should be demonstrated. These biomarkers include the protein and metabolite markers IFN- $\alpha$ , IL-12p40, IL-10, IP-10, TNF- $\alpha$ , IL-6, and neopterin and markers of transcriptional responses (ISG15, OAS-1, MX1 and TLR7). Once criteria have been reached to determine an initial dose for MAD, and there is evidence that the next higher dose is also well-tolerated as a single dose, then the MAD part will be initiated at the defined dose level. HVs will be screened up to 28 days before randomization into the MAD portion of this study. Only doses covered by the dose range evaluated in the SAD part will be used in the MAD part. The MAD study in HVs will consist of approximately 3 dose levels (Figure 1). The cohort size will be eight subjects randomly assigned to RO7020531 and two subjects randomly assigned to placebo. Each cohort will include a minimum of two female subjects, with at least one female on active drug.

Subjects randomized in the MAD study will be asked to remain in the unit from Day -2 until Day 14 with QOD dosing initiated on Day 1. In total, seven QOD doses will be administered with the last dose given on Day 13. Subjects will be discharged on Day 14.

After completing 7 QOD doses, each subject in the MAD cohorts will return for an outpatient follow-up visit 7 days after the last dose. All subjects will have a follow-up phone call 28 days after their last dose. Subjects will be asked to report any AEs that occur during this period.

Upon safety review (see Section 3.1.2), dose-escalation will proceed in the MAD part of this study until a maximal tolerated dose (MTD) or a mean RO7011785 AUC of  $\sim 2.8 \mu\text{g} \cdot \text{h/mL}$  is reached, or until it is determined that a suitable dose evaluation has been made by the Sponsor. The maximum dose investigated in MAD will not exceed doses evaluated in the SAD part.

Dose-escalation decisions in the MAD may utilize a Continual Reassessment Method (CRM) and may be modified accordingly. Information gained in the MAD part in HVs will be used to guide dose-selection for the study in CHB patients.

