### **3.1.2.2 Part 2: Chronic Hepatitis B Patients**

The dose level for the starting dose and subsequent doses in patients will be defined based on a comprehensive review of available safety, PK and select PD data from the SAD and completed MAD cohort(s) in HVs by the IMC (see Section 3.1.3). The starting dose in patients will be lower than or equal to the dose that has been studied and has acceptable tolerability in the MAD part of the study, with evidence of PD effects in HVs (dose not higher than the MTD in HVs).

After the completion of dosing in Cohort 1 of Part 2, the decision on dose level for Cohort 2 will be taken by the IMC upon the review of data once all 10 patients have completed 6 weeks of treatment or have discontinued treatment prematurely (see Section 3.1.3). The IMC decision to open the next cohort will be acknowledged by the active investigators. Dose level selection after Cohort 1 may be guided by predictive models for safety as a function of dose. The dose levels for a subsequent cohort will not be higher than double compared to the previous cohort. The maximum dose in CHB patients will not exceed exposure documented with adverse effects in the monkey GLP toxicology studies.

The decision to open the optional Cohort 3 will be taken in the same fashion by the IMC upon the review of safety and tolerability in Cohort 2.

The dose for optional Cohort 4 has been predefined at the level of 150 mg QOD for 6 weeks. *For dose modifications in this cohort, see Section 4.4.2.3 and Section 5.2.1.*

The recommendation for the subsequent cohort dose level will be shared with the IEC/IRB. Exploration of doses beyond the maximum proposed dose level will not occur until approval is received from the IEC/IRB.

For stopping rules in patients, see Section 4.7.1.1.

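### Does the unspecified prior of an optional dose-escalation model leave the plan's "MTD" limits without meaning?

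*Combined protocol and SAP*

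**What the plan says.** All references are to the combined protocol and SAP.

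- **Section 3.1.1.2** (multiple ascending dose, MAD): "dose-escalation will proceed in the MAD part of this study until a maximal tolerated dose (MTD" opens a list of three alternatives. The others are a mean RO7011785 AUC of about 2.8 µg·h/mL and a Sponsor judgement that doses have been suitably evaluated.
- **Section 3.1.2.2** (patients): the starting dose may not exceed a dose studied and acceptably tolerated in the MAD part, with pharmacodynamic effect. A parenthesis adds "dose not higher than the MTD in HVs".
- **Section 6.10.2**: after each cohort the N-CRM is updated and "a new MTD will be defined as the dose such that" two conditions hold. The posterior probability of a dose-limiting event (DLE) rate between 20% and 35% is maximised, and "The probability of being within the excessive toxicity interval (above 35% DLE rate) is below 30" per cent. The priors for α and β "will be specified using the data from the already completed cohorts of the SAD part of the study". The reference dose is given as "ref, here equals to X mg, starting dose of MAD".
- **Status of the model, Section 6.10.2**: such approaches "will only be considered as supporting information for the dose-escalation and/or dose selection", and clinical judgement takes precedence. Two modelling approaches may be explored, and "Operating characteristics of both models will be compared to determine the appropriateness".

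**The concern.** MTD is absent from the abbreviation list, and the stopping rules in Section 3.1.2.1 never call their outcome an MTD. Read strictly, two limits refer to a quantity whose only computing rule belongs to an optional model. If the model is not run, the term has no stated rule behind it. If it is run, the result cannot be reproduced from the plan, because the form and weight of the prior, the list of single ascending dose (SAD) cohorts feeding it and the value of X are missing. Section 3.1.1.1 lets SAD and MAD overlap, so the set of completed cohorts can also change over time.

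There is a modelling worry too. Dose is the only covariate, yet the prior comes from one administration and the data from 7 (MAD) or up to 21 (patients). Section 3.2.1 expects both priming and tachyphylaxis, so the direction of any shift is unknown. A prior built on up to 64 active SAD subjects (8 cohorts × 8) could swamp a MAD cohort of 8 and weaken the overdose limit. At stake would be an inflated MTD, or a reported one that nobody could verify.

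**Working it through.** **The plan's own figure.** The one design probability that can be checked is in Section 6.1: the chance of at least one event in 8 patients at a 25% rate. 1 − 0.75⁸ = 0.8999, matching the stated 90%. No operating characteristic is given for the N-CRM.

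**Can the missing inputs matter?** The Section 6.10.2 model was evaluated on a grid. Inputs from the plan: the logistic form, the two MTD conditions, SAD doses of 3, 10, 20, 40, 60, 100, 140 and 170 mg, and 8 active subjects per cohort. Assumed, because the plan is silent: α ~ N(−1.5, 2²), log β ~ N(0, 1), reference dose 100 mg, no SAD DLEs, SAD likelihood raised to a weight w, and candidate doses equal to the SAD doses plus 150 mg. With DLE probability pᵢ at dose i and xᵢ DLEs among nᵢ subjects, the posterior is proportional to

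prior(α, β) × [∏ over SAD of pᵢ^xᵢ (1 − pᵢ)^(nᵢ−xᵢ)]^w × ∏ over MAD of pᵢ^xᵢ (1 − pᵢ)^(nᵢ−xᵢ).

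After one MAD cohort at 150 mg, the overdose limit first bars 150 mg at:

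| w | 100% | 50% | 25% | 10% | 0 |
|---|---|---|---|---|---|
| DLEs of 8 | never | 6 | 5 | 4 | 3 |

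Model MTD (mg) for assumed MAD results:

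| MAD DLEs | 100% | 50% | 25% | 10% | 0 |
|---|---|---|---|---|---|
| 3/8 at 100 mg | 170 | 170 | 150 | 100 | 60 |
| 0, 2, 4 of 8 at 100, 140, 150 mg | 170 | 170 | 150 | 140 | 140 |
| 0, 1, 2 of 8 at 100, 140, 170 mg | 170 | 170 | 170 | 170 | 170 |
| 0, 0, 3 of 8 at 100, 140, 170 mg | 170 | 170 | 170 | 170 | 170 |
| 0, 3, 0 of 8 at 100, 140, 170 mg | 170 | 170 | 170 | 170 | 170 |
| 0, 0, 3 of 8 at 100, 140, 150 mg | 170 | 170 | 170 | 170 | 170 |
| 0, 0, 3 of 8 at 60, 100, 140 mg | 170 | 170 | 170 | 150 | 140 |

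So the weight can matter a great deal in principle. The cohort list can too: at full weight with 3/8 at 100 mg (prior mean for α of ln(0.25/0.75) = −1.10), the MTD is 100 mg if SAD is complete through 100 mg and 170 mg if complete through 140 mg. The reference dose matters little. With 2/8 at 100 mg and no SAD data, values of 40, 60, 100 or 140 mg all give 100 mg.

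**Which rows resemble this trial?** Section 1.2.2 reports three healthy volunteers with events of the expected pharmacodynamic type, all above 100 mg and reversible. Counting all three as DLEs is an upper bound for that event type.

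- The first row puts DLEs at 100 mg, and the second needs 2 + 4 = 6. Neither fits.
- The last row tops out at 140 mg. Section 3.2.2.2 says patient Cohort 1 received 150 mg. If the Section 3.1.2.2 rule was followed, the top MAD dose was at least 150 mg, so this row does not fit either.
- The other four rows give 170 mg at every weight.

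**What operates without the model.** Section 3.1.2.1 stops escalation at three or more active subjects in a cohort with same-character events, or four across two consecutive cohorts. Three of eight is also where the overdose limit trips with no borrowing. If each subject's chance of such an event is 20%, P(X ≥ 3 of 8) = 0.203; at 50% it is 0.855. The AUC ceiling, the doubling limit, the Internal Monitoring Committee's decision and the halt at 4 of 15 discontinuations (Section 4.7.1.1) do not use the model either.

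**What is left to decide.** Section 1.2.2 reports 110 volunteers dosed, equal to the planned 80 + 30, and 30 patients in Cohorts 1 to 3. The Cohort 4 dose is predefined in Section 3.1.2.2.

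**The case for a change.** The best case for acting is that Version 7 still uses MTD as a limit, still allows added volunteer cohorts (Section 3.1.1.2), and does not record whether an MTD was reached, how, or at what value. A reader therefore cannot check the parenthesis in Section 3.1.2.2. Pooling single-dose and repeated-dose data is also a substantive choice. A DLE is defined by whether another administration would be prevented, which in SAD is a hypothetical judgement.

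The ambiguity about the word MTD stands, and so does the missing form and weight of the prior. The rest is weaker. The reference dose is identified in words, and its value could not be written before MAD doses were set during conduct (Section 4.4.2.1). A prior built from SAD data could not be given numerically before those data existed. The parenthesis in Section 3.1.2.2 follows a clause that already ties the starting dose to acceptable MAD tolerability, and Section 3.1.1.3 sets that limit without mentioning MTD.

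How much to borrow is a genuine trade-off. An overdose limit that trips from 3 of 8 would do so with probability 0.203, 0.321, 0.448 and 0.572 at true rates of 20%, 25%, 30% and 35%, all within the target interval. No weight is right by default, and the planned comparison of operating characteristics is a natural place to examine it.

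**Conclusion.** No change to the plan follows. The gap is missing detail about an optional, advisory model. Followed as written, the plan reaches its dose decisions through event counts, exposure, tolerability and committee review. In Sections 3.1.1.2 and 3.1.2.2 MTD can be read in its ordinary sense, as the highest dose found tolerable under those rules. If a model-based MTD is reported, a competent analyst would state that the N-CRM was used and give the priors, the SAD cohorts included and the reference dose. That is normal reporting and needs no amendment.

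In size, the unstated weight moves the model's MTD between 60 and 170 mg on the most sensitive hypothetical data. It does not move it in the four layouts that best match Part 1.

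This rests on assumptions: the base prior shown, no SAD DLEs, no more than three MAD DLEs, and a top MAD dose of at least 150 mg. The documents state neither the MAD doses nor the DLE counts. If a further volunteer cohort were opened with the model given real influence, its inputs would deserve a closer look then.
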